Stage 1 is focused on feasibility and does not include hypothesis testing. In Stage 2 trial, we will test two main hypotheses (1) SHIM clinics will have better adoption and penetration of HCV care elements, that will ultimately result in improved patient-level outcomes like HCV cure compared to standard of care; (2) Compared to No-ECHO, ECHO-facilitated sites will have improved HCV cascade outcomes.

The results of the model evaluation, if proven effective, will allow us to advocate for its scale-up to other non-specialized settings in Ukraine and internationally and contribute to HCV elimination.

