### 3.5.8 Analytic plan

All analyses will be according to the principle of intent-to-treat, i.e., analysis of site and individuals within the site as randomized. The primary individual-level outcomes are achieving three elements of the HCV treatment cascade (diagnosed, treated, achieving SVR). We have powered the study based on a comparison of the proportions among the three groups (see below). The denominator for all cascade indicators is the number of OAT patients who are screened positive for HCV and are enrolled in the study. The numerators, the number who completed the pre-treatment evaluation, started DAA treatment and achieved SVR, will be obtained from the electronic clinical data collection system. Data will be assessed for missingness. A repeated measures likelihood based mixed model with missing at random (MAR) assumptions will be used for the analysis of the primary outcome to compare the three allocations, adjusted for the stratification variables (geographic region) plus age and gender. We will also adjust for covariates that are predictive of missingness to be consistent with the MAR assumption. Sensitivity analyses as described below will be done to assess this assumption, which is a reasonable starting point given missing data is expected to be low. Results will be displayed as point estimates with corresponding 95% confidence limits. The primary (and secondary) outcomes will be tested at the 5% (2-sided) significance level.

Hypotheses

1) OAT facilities implementing the simplified integrated model will have adoption and penetration of HCV care elements, that will ultimately result in improved patient-level outcomes like HCV cure compared to standard of care (SOC);

2) Compared to No ECHO, clinicians at ECHO-facilitated sites will have improved HCV care cascade outcomes.

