In addition, we have planned to test for a linear trend among the intervention levels for the proposed outcomes, testing that SHIM+ECHO > SHIM with No ECHO > SOC. We also plan to test the treatment effects using similar methods for OAT dropout strata separately. In addition to direct effects, mediation and moderation regression will be conducted as described by Donaldson. Testing will be conducted at a Bonferroni corrected type I error level of 0.025 to control for multiple testing. Secondary and process outcomes will similarly be tested. These measures and their subscales will be compared as pre/post and over time using one-way ANOVA/Duncan test, with general linear models to identify differences in treatment effect stratified by the geographic region (cluster). Mean scores will be normalized, with comparisons between the three groups, with the referent being SOC. To address multiple testing, we will use the Benjamini-Hochberg method of controlling the false discovery rate. We do not expect missing data to be a concern since most of the data on primary outcomes will be derived from clinical source documentation; for the survey data, we expect that we will collect more than 90% of the data at the 24-week time point. We will, however, explore all patterns of missing data and compare those with and without data to determine whether the data may be MAR or not MAR (i.e. eliminate the missing completely at random assumption). We will conduct sensitivity analyses using an appropriate missing data method, such as multiple imputation.

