### 3.5.9 Power Analysis

We will need a sample size of 133 per group (total sample size of 399), to have 90% power at a 5% level of significance to detect a standardized effect size of 0.20 for a null hypothesis of no difference between the proportions in the three groups versus an alternative of at least one difference at the 24-week time point. Additionally, we will have 94% power with a 2.5% type I error rate (Bonferroni corrected) to detect a standardized effect size of 0.32 within each geographic strata. Conservatively, we expect a 10% loss of information at the 24-week time point. Therefore, we have inflated the sample size by 10% and will recruit a total of 480 patients for the Aim 3 outcomes.

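### Section 3.5.8 gives both 5% and an unassigned Bonferroni level of 0.025, and neither controls the family-wise error at 5% across three primary outcomes and two hypotheses

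*Combined protocol and SAP*

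**What the plan says.** Section 3.5.4 lists three primary endpoints, all on the same footing: completing the pretreatment evaluation (P1), starting DAA treatment (P2) and SVR12 (P3). The Summary says "In Stage 2 trial, we will test two main hypotheses": SHIM against standard of care, and ECHO against no ECHO. Section 3.5.8 repeats both hypotheses.

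Three statements on error control stand in section 3.5.8:

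- "The primary (and secondary) outcomes will be tested at the 5% (2-sided) significance level".
- After the linear-trend, OAT-dropout-strata and mediation analyses: "Testing will be conducted at a Bonferroni corrected type I error level of 0.025 to control for multiple testing". The next sentence is "Secondary and process outcomes will similarly be tested".
- After the text on subscales, ANOVA with Duncan's test, and mean scores: "To address multiple testing, we will use the Benjamini-Hochberg method of controlling the false discovery rate". No false discovery rate level and no family of tests is given.

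Section 3.5.9 asks for "a sample size of 133 per group (total sample size of 399), to have 90% power at a 5% level of significance", and uses 2.5% for power within a region.

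No sentence ranks P1 to P3, sets a testing order, or says whether the trial succeeds on one, two or all three.

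**The concern.** The 5% sentence names the primary outcomes. The 0.025 sentence is general and does not exempt them. An analyst who follows the first would declare a primary result with p = 0.03 significant; one who follows the second would not. Both could say that they kept to the plan.

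A second problem remains whichever level is chosen. Since 0.025 = 0.05/2, it allows for two tests. That fits two hypotheses on one outcome, but there are three primary outcomes. Without an order or a success rule, each added outcome is a further chance of a false positive claim. At stake is whether a reported primary success carries the 5% error rate that a reader would assume.

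**Working it through.** **Inputs from the documents.** Three primary outcomes (3.5.4), two hypotheses (Summary, 3.5.8), levels of 0.05 and 0.025 (3.5.8), 160 patients per arm (3.5). Six tests = 3 × 2.

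**Assumption.** The documents give no expected cascade rates, so those used below are assumed and varied.

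**Step 1: the plan's own figure.** Take the section 3.5.9 calculation as a chi-square test of three proportions (2 df) with standardized effect w = 0.20 and 90% power, so N = λ/w², where λ is the required non-centrality.

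- At 5%: λ = 12.65, N = 12.65/0.04 ≈ 317.
- At 2.5%: λ = 14.75, N ≈ 369.

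Neither gives the stated 399. Section 3.5.9 therefore does not show which level, or which test, was used.

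**Step 2: independent tests under no effect.** The chance of at least one false claim among k tests is 1 − (1 − α)^k.

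| Family | at 0.05 | at 0.025 |
|---|---|---|
| 2 hypotheses, one outcome | 1 − 0.95² = 9.75% | 1 − 0.975² = 4.9% |
| 3 outcomes, one test each | 1 − 0.95³ = 14.3% | 1 − 0.975³ = 7.3% |
| 3 outcomes × 2 hypotheses | 1 − 0.95⁶ = 26.5% | 1 − 0.975⁶ = 14.1% |

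So 0.025 works for two hypotheses on a single outcome and fails across three.

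**Step 3: allowing for correlation.** P1 to P3 are nested, so the values in step 2 are too high. Simulation with 160 per arm, no effect, patient-level tests and no clustering: both SHIM arms against SOC, and SHIM+ECHO against SHIM, on each outcome. The last column uses 0.025/3 = 0.0083, which is the first Holm step within each hypothesis.

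| Assumed P1 / P2 / P3 | any of 6 at 0.05 | any of 6 at 0.025 | any of 6 at 0.0083 |
|---|---|---|---|
| 60 / 45 / 36% | 19.7% | 10.8% | 3.8% |
| 50 / 35 / 24.5% | 20.4% | 10.9% | 4.1% |
| 70 / 56 / 44.8% | 20.3% | 11.4% | 4.0% |
| 80 / 72 / 64.8% | 19.1% | 10.3% | 3.7% |
| 60 / 30 / 24% | 21.2% | 11.5% | 4.1% |
| 70 / 66.5 / 63.2% | 15.8% | 8.5% | 3.1% |

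About 17–20% and 9–11% is a fair summary; the extremes tried reach 16–21% and 8–11%. Every scenario exceeds 5% at both levels.

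**Step 4: a smaller family.** If the primary analysis is one three-arm test per outcome (three tests), similar simulations give about 9–11% at 0.05 and 5–6% at 0.025, and about 8% and 4% in the most tightly nested cascade.

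**Step 5: Benjamini-Hochberg, if it were applied to the six primary tests.** With an assumed rate of 0.05, the chance of a false claim is about 4–4.5% when no hypothesis has an effect. With independent tests it rises to about 8–10% when one to four of the six effects are real. That is not strong family-wise control.

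**The case against.** The best defence is that the statements have different scopes. The 0.025 sentence follows the trend, dropout-strata and mediation analyses, and section 3.5.9 attaches 2.5% to regional strata. One could read 5% for the main comparison and 0.025 for the additional ones. Benjamini-Hochberg follows text on subscales and mean scores, which the binary primary outcomes do not have, so it appears to concern secondary measures. This is plausible, and the reading of Benjamini-Hochberg is accepted here. But the plan does not state these scopes, and on this reading the primary outcomes stay at an unadjusted 5%, the worse of the two levels.

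It is also fair that six tests is a reading. Section 3.5.8 speaks of comparing three allocations, and the power null in 3.5.9 is a three-group one. With three such tests, 0.025 roughly suffices; 5% does not.

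Three stronger conclusions might be inferred, and the documents do not support them.

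- That none of the plan's procedures controls the error at all. Benjamini-Hochberg stays below 5% when nothing works; what it lacks is strong control.
- That the trial was secretly sized at a further level, 0.05/3 = 0.0167. That level does give N = 398.7 in step 1, but it is a back-fit. A pairwise comparison with d = 0.40 at the stated 5% needs 132.3, so 133 per group and 3 × 133 = 399. Neither reading fits the text fully.
- That one success among six would be claimed as proof. No success criterion is stated. If all three outcomes were required, there would be no inflation across outcomes.

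**Conclusion.** The point holds. Section 3.5.8 contains two levels that can both be applied to a primary outcome, and neither keeps the family-wise error at 5% across three outcomes and two hypotheses.

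The exact size depends on assumed cascade rates, on ignoring clustering by clinic, and on counting six tests. The direction does not depend on the rates: both levels exceeded 5% in every six-test scenario tried. The planned test of linear trend ("we have planned to test for a linear trend among the intervention levels for the proposed outcomes") is not counted and could only add to the error if treated as confirmatory. With three three-arm tests the excess at 5% remains, while 0.025 is close to adequate.

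This is a defect of specification. It does not show that the trial would claim success wrongly, or that a particular unstated level was used for the sample size.

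**What to change.** Before outcomes are analysed by arm:

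- State one rule for the primary family. One option is 0.025 for each hypothesis with Holm across P1, P2 and P3 within it, giving about 3–4% under no effect. A pre-specified testing order, or a requirement that all three outcomes succeed, would also be valid. The choice belongs to the sponsor.
- Delete the 5% sentence as it applies to primary outcomes, and name the tests that 0.025 covers.
- State that Benjamini-Hochberg covers secondary and process outcomes only, and give its level.
- In section 3.5.9, name the test, the definition of the effect size and the level behind 399, and make them match 3.5.8.

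The change is to wording only and needs no new data. The price of the Holm option is a stricter first threshold, 0.0083 in place of 0.05 or 0.025. As a rough guide, take the 2-df test with w = 0.20 and 480 × 0.9 = 432 evaluable patients: power falls from 96.9% at 0.05 to 88.6% at 0.0083. Both figures ignore clustering, so they are upper bounds.

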### 3.4.3 Quantitative Assessment of Organizational Factors

During the main phase of the project, OAT site staff and administrators (average N=3 per site) will complete a survey at baseline and the end of follow-up phase. Provider-level Factors will include provider characteristics (e.g., socio-demographics, education and work experience) and their attitudes toward SHIM (or a theoretical integrated HCV care model at the SOC sites) and their

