level of self-efficacy implementing SHIM. Attitudes and stigma towards drug users with and without HIV and HCV will be assessed using feeling thermometers operationalized as stereotypical beliefs, attribution beliefs, expectations with regard to rehabilitation chances and social distance [26], and previously used to compare attitudes over time as clinicians gain more contact and experience [27]. For Organizational Factors, clinic administrators will be asked to complete brief surveys on organizational characteristics (number, type, and turnover of staff, types of services provided, hours spent on clinical and administrative tasks, budget). Routine organizational assessments to gauge the progress of implementation and identify areas for future growth are conducted initially by improvement coaches with transfer of implementation to the country team. To understand the organizational changes, we will also have clinic staff and administrators complete several brief validated scales twice annually using REDCap: Organizational Capacity Inventory (e.g., perceived organizational climate, norms, trust and communication) and Organizational Readiness to Change Scale [28] and Organizational Functioning Scale [28]. These brief organizational measures include standardized scales for Social Dominance Orientation [29], which assesses the differences in how staff perceive themselves as “superior” to their patients and often observed in addiction treatment ( $\alpha > 0.90$ ); Resistance Towards Change [30], which assesses how staff respond to innovation within an organization ( $\alpha > 0.90$ ). Discrimination toward OAT patients with HCV by staff will be measured using feeling thermometers [31], which assesses the extent to which staff members believe that individuals should be treated differently for their mental illness (a weakness) and related activities ( $\alpha > 0.85$ ; including subscales) [32], that assesses staff attitudes toward mental illness; as well as additional attitudes that we have created that include information, motivation and necessary skills needed for integration of SHIM into OAT settings and towards provision of HCV services. A review of policies and procedures (and changes) will be used to assess Community-level Factors, including types of services available, geographic proximity of treatment and prevention services, and perceived barriers from patients to accessing services (e.g., hours of service, transportation) from Aim 2. Structural factors will include indicators of policing (i.e. frequency of arrests); incarceration, stigma and discrimination experienced by participants.

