### 3.5.1 Design overview

Individual randomization of subjects within each site would likely lead to a high degree of cross-contamination between the study groups because the selected interventions are designed to sustainably change the provider knowledge and practice. Therefore, we have chosen a cluster-randomized trial design, where participating sites will be randomly assigned to one of the three implementation arms. Based on our preliminary studies suggesting region-specific differences in HCV level among OAT patients, we will stratify 12 OAT sites by 4 defined geographic regions (Center, East, South, West) at a 1:1:1:1 ratio. To achieve the desired sample size (see Sample Size section) and retain equal size in each group, we will select and match 3 clinics across the 4 regions. One clinic per triplet will be randomized to one of the three arms: Standard of Care, SHIM and SHIM+ECHO (see Study Conditions), resulting in total 4 clinics per arm. Each clinic will aim to recruit 40 patients. In case of clinic's capacity the availability of DAA medication in region, the clinic's capacity to include in treatment and monitor the course of treatment of a larger number of patients) the number of participants can be increased up to 60). All sites will follow the same patient recruitment and data collection procedures.

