Aim 3's analysis will involve three distinct strategies. First, we will examine the time difference in HCV cascade elements (% diagnosed, % treated, % achieving SVR), with sub-analyses for geographic area and OAT dropout +/- ECHO vs SOC setting. To do this, we will use a generalized mixed linear model (with a logit link), where group will vary by either study arm or by geographical area. Our dependent variables will include: 1) a binary indicator for whether an individual patient achieved the desired HCV diagnosis/treatment coverage cut-off (e.g. diagnosis coverage >80%), as previously used to measure comprehensive and holistic integrated primary care for PWID receiving buprenorphine [42]. The same approach will then be used for secondary individual outcomes (treatment motivation and adherence, treatment satisfaction, quality of life), which we have done previously when integrating addiction treatment into specialty services in the US [43] and Ukraine [12]. 2) treating the primary and secondary indicators as a continuous variables. Any changes in national guidelines that might influence HCV treatment availability would not be scored until after at least 1 year after publication in order to allow for uptake changes by clinicians. Our covariates will include time trends, client-level variables including demographic characteristics, fibrosis stage, treatment motivation and adherence, addiction severity and mental health measures, as well as organizational and provider level measures (from Aim 2).

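### The Aim 3 logit-link model takes an uncapped set of clinic-level covariates from Aim 2, although 12 clinics leave only 6 clinic-level degrees of freedom for comparing arms

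*Combined protocol and SAP*

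**What the plan says.** **Design (3.5.1).** Clinics are the randomised unit: "we will stratify 12 OAT sites by 4 defined geographic regions (Center, East, South, West) at a 1:1:1:1 ratio". Then "One clinic per triplet will be randomized to one of the three arms", "resulting in total 4 clinics per arm". On size, "Each clinic will aim to recruit 40 patients", which may rise to 60.

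**Two models for the same outcomes (3.5.8).** The section opens with a mixed model for the primary outcome that compares the three allocations, "adjusted for the stratification variables (geographic region) plus age and gender", plus covariates that predict missingness. It then sets out three strategies for Aim 3. The first is a generalized linear mixed model with a logit link for the proportions diagnosed, treated and reaching SVR. Its covariates are time trends and a list of patient variables, "as well as organizational and provider level measures (from Aim 2"). No number, selection rule or time point is given for these measures. The section does not rank the two models.

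**Where the measures come from (3.4.1, 3.4.3).** "clinic administrators will be asked to complete brief surveys on organizational characteristics": staff number, type and turnover, services, hours and budget. In addition, "OAT site staff and administrators (average N=3 per site) will complete a survey at baseline and the end of follow-up phase", and several scales are completed twice a year. The provider-level factors include self-efficacy in delivering SHIM and fidelity to SHIM and ECHO.

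**Data reduction (3.4.4).** Principal components are planned for these variables in the Aim 2 analysis. The number to be kept is not stated.

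**The concern.** Arm is a property of the clinic, so the arm effect is estimated from differences among 12 clinics, however many patients each one recruits. A covariate with one value per clinic draws on the same 12 points. The plan adds such covariates without limit, to a model for the outcomes that decide whether SHIM and ECHO work.

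Two things are at stake. The first is precision: a handful of clinic-level terms can make the arm comparison uninformative, and the result then depends on which measures happen to be entered. The second is bias. Self-efficacy in SHIM, fidelity to SHIM and ECHO, and the later rounds of the scales are measured after allocation and may be changed by it. Fidelity has no clear meaning in the standard-of-care arm. The staff attitude item asks about SHIM at SHIM sites and about a hypothetical model at standard-of-care sites, so it differs by arm even at baseline. Adjusting for variables of this kind can take out part of the effect under test.

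**Working it through.** **Inputs.** From 3.5.1: 12 clinics, 3 arms, 4 regions, one clinic per arm in each region, 40 patients per clinic (12 x 40 = 480, the planned total). From 3.5.8: two-sided 5% level. The documents state no clinic-level degrees of freedom, so there is no figure of the plan's own to reproduce here.

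**Degrees of freedom.** Clinics - intercept - (arms - 1) - (regions - 1) = 12 - 1 - 2 - 3 = 6. With k covariates constant within clinic, 6 - k remain.

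**Number of candidates.** The clinic characteristics in 3.4.3 are staff number, staff type, staff turnover, services, clinical hours, administrative hours and budget: 7, or 6 if hours count once. The scales come on top, so the pool exceeds 6 on either count.

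**Cost per covariate.** With no covariate, the variance of an arm contrast is (1/4 + 1/4) = 0.5 times the clinic-level residual variance. Let the k covariates be normal and unrelated to arm and outcome. After the intercept, region and the other arm term are removed, 12 - 1 - 3 - 1 = 7 dimensions remain. The share R² of the arm contrast that the covariates absorb then follows a Beta(k/2, (7 - k)/2) distribution. The variance inflation is 1/(1 - R²), and

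width ratio = sqrt(median inflation) x t(0.975, 6 - k) / t(0.975, 6), with t(0.975, 6) = 2.447.

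| k | df left | t(0.975) | median variance inflation | width ratio |
|---|---|---|---|---|
| 0 | 6 | 2.447 | 1.00 | 1.00 |
| 1 | 5 | 2.571 | 1.09 | 1.042 x 1.051 = 1.09 |
| 2 | 4 | 2.776 | 1.32 | 1.149 x 1.135 = 1.30 |
| 3 | 3 | 3.182 | 1.71 | 1.306 x 1.301 = 1.70 |
| 4 | 2 | 4.303 | 2.42 | 1.555 x 1.758 = 2.73 |
| 5 | 1 | 12.706 | 4.13 | 2.032 x 5.193 = 10.6 |
| 6 | 0 | none | 12.7 | no interval |
| 7 | none | none | not estimable | not estimable |

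Simulation of the 12-clinic design agrees with the formula to within sampling error (ratios of about 2.7 to 2.8 at k = 4 and 10 to 11 at k = 5). At k = 7 the clinic-level design matrix has 13 columns and rank 12, and the arm contrasts were estimable in none of the draws. For k = 0 to 6 they were estimable in all of them.

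**Measures that vary within clinic.** In a 480-patient design matrix, 8 provider measures that differ among 3 providers per clinic left full column rank (6 + 8 = 14 of 14). Measures of that kind do not alias arm.

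**The case against.** A reader might infer that the covariates named in 3.5.8 use up all 6 degrees of freedom, so that the SHIM and ECHO effects cannot be estimated at all. The documents do not support that, for four reasons.

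- **The number of terms is not given.** With one or two clinic-level covariates the loss is modest. With up to six a point estimate still exists. Non-estimability needs seven or more.
- **The region, age and gender model does not name these measures.** As described, that arm comparison keeps its 6 degrees of freedom.
- **Not every measure need be constant within clinic.** About three people per site respond, surveys are repeated, and the Aim 2 model in 3.4.4 separates provider from site. Measures that vary within clinic need not each cost a degree of freedom.
- **Principal components could shrink the set.** The measures come from Aim 2, where this reduction is planned.

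A strongly prognostic covariate could also reduce the clinic-level residual variance and repay some of its cost.

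These points limit the claim but do not remove the problem. The logit-link model analyses the same three outcomes, and nothing makes it subordinate. Section 3.5.2 allows a site to have a single narcologist, so many provider measures will be constant or nearly so within a clinic, and the clinic characteristics describe the clinic by definition. Measures that vary over time do so through values taken after randomisation. The Aim 3 text does not invoke principal components, and even 3 or 4 of them would widen the interval about 1.7 or 2.7 times.

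**Conclusion.** The point holds for the logit-link model. It adds an unlimited set of Aim 2 measures to a comparison that has 6 clinic-level degrees of freedom, and the pool of candidates is larger than 6. The cost runs from about 1.1 times the interval width with one clinic-constant term to 10 to 11 times with five. Inference is lost at six and the arm effect itself at seven. How far along this range the analysis would fall cannot be determined, because the plan does not name the terms. The possible bias from post-randomisation or arm-dependent measures is a separate harm and applies even to a single such covariate.

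The width ratios assume covariates constant within clinic, unrelated to arm and outcome, a fixed clinic-level residual variance, and a linear clinic-level approximation to the logit model. They also assume inference that respects clinics as the randomised unit. The Aim 3 text names neither a clinic random effect nor a small-sample method, so a large-sample analysis could hide the loss behind standard errors that are too small.

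**What to change.** In 3.5.8, remove the Aim 2 organizational and provider measures from the covariates of the Aim 3 arm comparisons. Alternatively, allow at most one pre-specified clinic-level covariate measured before randomisation, such as OAT caseload. Keep the other measures for the exploratory Aim 2 analysis and the mediation and moderation analyses.

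State that the confirmatory comparison of arms uses arm, region, age and gender, and that the logit-link analyses with further covariates are supportive. Any clinic-level variable brought in as a predictor of missingness should count against the same limit of one.

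The cost is a few sentences of SAP wording, with no new data and no patients. The downside is losing possible adjustment for chance imbalance between clinics, which 12 clinics can barely support in any case. The change should be made before outcome data are compared by arm.

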#### 3.4.5 Power Analysis

The qualitative sub-study sample during the pilot phase will be limited to one focus group with patients and three in-depth interviews with providers.

In the main phase, we will conduct two focus groups with 6-8 patients, one in-depth interview with participant who have dropped out of treatment, or not completed SVR12 testing, or didn't start treatment, two in-depth interviews with 2-4 providers.

In order to conduct the proposed analysis, a sample size of 900 patients, provides more than sufficient power to conduct the proposed analyses. The use of principal component analysis (PCA), for parsimoniously grouping variables is a reductionist strategy to explain groupings of variables with multiple collinearity. The time-dependent analysis allows for detection of even small changes in the primary and secondary outcome, even if the primary (or secondary) outcome increases any of the study groups. Thus, as few as 200-300 participants in each group is more than sufficient to achieve sufficient power (>0.95) to detect an intervention effect, including a synergistic effect of intervention^[No ECHO] x intervention^[ECHO] and even by site type (by varying degrees of integration), over time.

### 3.5 Research methods for Aim 3

Aim 3: To evaluate the effectiveness of SHIM in improving the HCV treatment cascade outcomes using a cluster-randomized three-arm trial design in 480 HCV-infected patients at 12 OAT clinics

randomized to standard of care (N=160) versus SHIM with (N=160) or without (N=160) ECHO facilitation.

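### The supplementary linear-trend test is described as testing SHIM+ECHO > SHIM > SOC, but with equal arms it compares SHIM+ECHO with SOC, and no SHIM+ECHO versus SHIM contrast is named for the primary outcomes

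*Combined protocol and SAP*

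**What the plan says.** Section 3.5.8 (Analytic plan) lists two hypotheses. The first is that SHIM sites do better than SOC. The second reads "Compared to No ECHO, clinicians at ECHO-facilitated sites will have improved HCV care cascade outcomes". The primary analysis is a mixed model comparing the three allocations, reported as estimates with 95% confidence limits. No individual contrast is named.

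Later in 3.5.8, as an addition to that model, the plan will "test for a linear trend among the intervention levels for the proposed outcomes, testing that SHIM+ECHO > SHIM with No ECHO > SOC". It gives no arm scores and no rule for when the ordering may be claimed.

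Two significance levels appear in 3.5.8. One sentence says "The primary (and secondary) outcomes will be tested at the 5% (2-sided) significance level". The paragraph with the trend test states a Bonferroni level of 0.025.

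The planned arms are equal. The Aim 3 statement that opens section 3.5 has patients "randomized to standard of care (N=160) versus SHIM with (N=160) or without (N=160) ECHO facilitation", and 3.5.1 has clinics assigned to "Standard of Care, SHIM and SHIM+ECHO (see Study Conditions), resulting in total 4 clinics per arm". On clinic size, 3.5.1 says "Each clinic will aim to recruit 40 patients", with the allowance that "the number of participants can be increased up to 60". The calculation in 3.5.9 is for a null of "no difference between the proportions in the three groups versus an alternative of at least one difference".

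**The concern.** The ordering attached to the trend test contains two statements: SHIM beats SOC, and SHIM+ECHO beats SHIM. The second is hypothesis 2 and the reason for a third arm. A linear-trend test has a different null, a zero slope across the arm scores, and one slope cannot establish two separate inequalities.

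The rest of the plan does not clearly fill the gap for the cascade outcomes. The mixed model names no contrast, and SOC is the only referent mentioned. The Duncan comparisons, which could set SHIM+ECHO against SHIM, are attached to secondary and process measures. So the only named test tied to SHIM+ECHO > SHIM on the primary outcomes gives the SHIM arm no weight. If SHIM works well against SOC, a significant trend is likely whatever ECHO does. Taken at its wording, that result could be cited for ECHO in scale-up decisions without evidence that ECHO adds to SHIM.

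**Working it through.** **The plan's own figures.** None is given for the trend test. The 133 per group in 3.5.9 belongs to the three-group test. Read as a 2-df chi-square with Cohen's w = 0.20, 5% level and 90% power, its inputs give 106 per group (317 in total). The figure of 133 (399) is reproduced exactly at a level of 0.05/3. Nothing below depends on it.

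**Step 1: weights.** With scores s = 0, 1, 2, the trend statistic weights arm i by n_i(s_i - s̄).
- Arms of 160: s̄ = 1, weights (-160, 0, +160), that is (-1, 0, +1).
- SOC at 240 (four clinics of 60), others 160: s̄ = 480/560 = 0.857, weights (-205.7, 22.9, 182.9), scaled (-1, 0.11, 0.89).
- Only the SHIM arm at 240: the SHIM weight is still 0.

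So the allowance of up to 60 per clinic changes little. This step needs no assumed response rates.

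**Step 2: patient-level check.** For n per arm, power ≈ Φ{[(p3 - p1) - 1.96·SE0]/SE1}, with SE0 = √[p̄(1 - p̄)·2/n] and SE1 = √{[p1(1 - p1) + p3(1 - p3)]/n}. Take n = 160, SOC 40%, SHIM+ECHO 60%, two-sided 0.05, clustering ignored.
- SHIM 60%: p̄ = 0.533, SE0 = 0.0558, SE1 = 0.0548; Φ(1.66) = 95.1%.
- SHIM 80%: p̄ = 0.60, SE0 = 0.0548; Φ(1.69) = 95.5%.
- SHIM 40% or 50%: 95.1%.
- Plain two-arm test of SOC versus SHIM+ECHO: 95.1%.

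The position of SHIM alone makes almost no difference, because it enters only through the variance. A logistic slope behaves the same way: z = 3.55, 3.56 and 3.62 for 40/50/60, 40/60/60 and 40/80/60.

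**Step 3: clinic-level rates.** The documents give no response rates or ICC, so both are assumed here. The simulation uses 20,000 trials per scenario, 4 regions × 3 arms, clinics of 40, beta-binomial counts and a region + arm ANOVA of clinic proportions with (4 - 1)(3 - 1) = 6 residual df. Rejection is in the stated direction. Repeat runs differ by one or two percentage points.

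| True SOC/SHIM/SHIM+ECHO | Rule | ICC 0.01 | ICC 0.05 | ICC 0.10 |
|---|---|---|---|---|
| 30/60/60 (ECHO adds nothing) | trend, 0.05 | 97% | 77% | 55% |
| 30/60/60 | trend, 0.025 | 92% | 62% | 41% |
| 30/60/60 | both adjacent contrasts, 0.05 | 3% | 2% | 1% |
| 30/70/60 (SHIM alone better) | trend, 0.05 | 98% | 78% | 58% |
| 30/70/60 | both adjacent contrasts, 0.05 | under 0.5% | under 0.5% | under 0.5% |

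If clustering is ignored, the trend test rejects in about 100% of trials in both scenarios.

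Hand check of the first row: the design effect 1 + 39·ICC is 1.39, 2.95 and 4.90. The expected difference over its standard error is 0.30/√[design effect × (0.21 + 0.24)/160] = 4.80, 3.29 and 2.56, against a critical t (6 df) of 2.45. That agrees with high, moderate and just-over-half rejection.

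**Step 4: cost when the ordering is true.** With assumed rates of 30/45/60%, both adjacent contrasts succeed in about 58% of trials if clustering is ignored. At clinic level they succeed in about 26%, 7% and 3% at 0.05, and about 15%, 4% and 1% at 0.025, for the three ICCs.

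**The case against.** The trend test is an addition to a three-arm model whose estimates and intervals will be reported, so a reader would see if SHIM+ECHO were level with or below SHIM. Hypothesis 2 is listed separately, and an ordered alternative is a common shorthand for a trend test. This stands, and it limits the seriousness. A reader might infer that the plan uses the trend result to decide hypothesis 2 or to confirm the ordering. The documents do not support that, because they set no such rule. The defect is that the test is described as testing something it cannot test, while the contrast that could is not named.

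It might also be inferred that the trend test rejects whatever happens. It does not. The false impression arises only when SHIM+ECHO truly exceeds SOC; if those two arms are equal, the test keeps its nominal error.

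Nor is the three-group test in 3.5.9 at fault. It states openly that its alternative is any difference. It simply cannot serve as evidence for hypothesis 2.

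Two further objections hold. Figures at two-sided 0.05 alone would overstate the size, since the same paragraph gives 0.025. And the two-contrast rule is costly with four clinics per arm. That does not rescue the trend test, whose higher rejection rate is power for SHIM+ECHO versus SOC and not for the ordering.

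**Conclusion.** The point holds as one of wording and interpretation for a supplementary test, together with a missing contrast for hypothesis 2. It should be fixed; it does not undermine the primary model. The zero weight is algebra and rests on equal arms (planned) and equally spaced scores (assumed as the ordinary meaning). The size rests on assumed rates and ICCs: when ECHO adds nothing at 30/60/60%, the clinic-level trend is significant in roughly 55-97% of trials at 0.05 or 41-92% at 0.025, against 1-3% when both adjacent contrasts are required at 0.05. Smaller SHIM effects shrink these figures: at 30/50/50% the clinic-level range is about 29-74% at 0.05 and 19-58% at 0.025.

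**What to change.** In 3.5.8:
- Name two contrasts from the planned primary model for the cascade outcomes, SHIM versus SOC and SHIM+ECHO versus SHIM, each reported with its confidence interval.
- Test both at one stated level, reconciling the 5% and the 0.025 now in the section.
- Base any claim for hypothesis 2 on the SHIM+ECHO versus SHIM contrast. Claim the full ordering only if both contrasts are significant in the stated direction; that joint claim needs no further alpha adjustment.
- Drop the trend test, or keep it labelled as essentially SHIM+ECHO versus SOC. State that neither it nor the three-group test is evidence that ECHO adds to SHIM.

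This takes a few sentences and no new data. The real cost is the much lower chance of claiming the full ordering shown in step 4 of the working. The sponsor should know before reporting that, with four clinics per arm, the design has little power for that joint claim unless the ICC is very small or the effects are large.
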